#### 9.5.4.8 Assessment of Gout Flare

There is no validated instrument to assess gout flares. Gout flares will be assessed by asking subjects the following questions at the time points specified in Section 2.1. To be considered a gout flare, subjects must answer positively to 3 of the following 4 questions [Gaffo et al. 2012]. PRIVATE AND CONFIDENTIAL INFORMATION OF HORIZON THERAPEUTICS IRELAND DAC Page 77 of 129

Protocol: HZNP-KRY-201

KRYSTEXXA IND: 010122

Version 3.0, Administrative Change 1

- 1. Have you had a gout flare in your joints in the last 2 weeks (Screening Visit only) or since last visit (all other visits)? (Yes/No)
- 2. If yes to flare, was there pain in the joint(s) that was different than normal? (Yes/No)
- 3. If yes to flare, was there pain in the joint(s) at rest that was greater than a 3 out of 10 (where 0 = no pain and 10 = the worst pain imaginable)? (Yes/No)
- 4. If yes, was there swelling in the joint(s)? (Yes/No)

Additionally, the subject should report:

- the joints affected using a subject-facing diagram (see Appendix 17.6);
- the therapy taken to treat the gout flare (part of standard AE assessment);
- how long the gout flare lasted and when it resolved (part of standard AE assessment).

Each confirmed flare will be captured in the eCRF to allow summary of the number of flares. Intensity of gout flares will be documented. Gout Flares should be captured as an Adverse Events/Serious Adverse Event (see 9.5.4.1)

### 9.5.5 Appropriateness of Measurements

The study population is well-defined and is consistent with the expected target population for whom pegloticase is indicated (adult subjects with uncontrolled gout and with the ability to tolerate MTX).

### 9.5.6 Study Procedures

Subjects who provide informed consent and who meet all the entry criteria for participation in this study will be enrolled.

## 9.5.6.1 Screening/MTX Run-in Period

During the Screening /MTX Run-in Period, study candidates will be evaluated for study entry according to the stated inclusion and exclusion criteria (Section 2.1). The following procedures will be performed during screening to establish each candidate's eligibility for enrollment into the study.

# 9.5.6.1.1 Screening Visit (Within 2 Weeks Prior to the First Dose of MTX at Week -4)

- Obtain signed, written informed consent. Refusal to provide this permission excludes an individual from eligibility for study participation. Record date informed consent was given and who conducted the process on the appropriate source documentation.
- Determine study eligibility through review of the inclusion/exclusion criteria (see (Section 9.3).
- Collect complete gout history (on gout-specific CRF), other relevant medical/surgical history, and medication history, including gout medications starting at the time of

KRYSTEXXA IND: 010122 Protocol: HZNP-KRY-201 Version 3.0, Administrative Change 1

diagnosis and up to screening (on gout medications-specific CRF), substance use history. History of non-gout medication use in the year prior will be collected (see Section 9.4.9 for restrictions regarding medications).

- Assess for the presence of tophi.
- Obtain demographic information.
- Perform a complete physical examination.
- Document gout flares and intensity.
- Record vital signs (blood pressure, respiratory rate, temperature, and heart rate), including measurements of height and weight (see Section 9.5.4.4).
- Obtain blood samples for hematology and clinical chemistry analysis.
- Obtain a urine sample for uric acid:creatinine ratio.
- Obtain a serum sample from all females of childbearing potential for performance of a pregnancy test.
- Obtain blood samples to evaluate sUA (only 1 sample for central laboratory), G6PD, and HIV antibody.
- Administer HAQ and record patient and physician global assessments and joint pain assessment responses.
- Inquire about AEs.

## 9.5.6.1.2 Week -4

- Confirm study eligibility through review of the inclusion/exclusion criteria (see Section 9.3).
- Collect medical/surgical history, substance use history, and medication history (see Section 9.4.9 for restrictions regarding medications).
- Perform a targeted physical examination should include heart, lungs and abdominal exam and joint and skin evaluation and assessment of AEs. Any finding will be recorded as an AE.
- Document gout flares and intensity.
- Record vital signs (blood pressure, respiratory rate, temperature, and heart rate) (see Section 9.5.4.4).

Protocol: HZNP-KRY-201 Version 3.0, Administrative Change 1

KRYSTEXXA IND: 010122

- Obtain blood samples for hematology and clinical chemistry analysis.
- Obtain a urine sample for uric acid:creatinine ratio.
- Obtain a urine sample from all females of childbearing potential for performance of a pregnancy test.
- Obtain a blood sample for measurement of sUA (only 1 sample for central laboratory).
- Collect swollen/tender joint counts; administer HAQ; and record patient and physician global assessments and joint pain assessment responses.
- Provide dosing calendar for subjects to record the date and time they take MTX (Additional calendar pages may be provided at future visits as needed).
- Dispense MTX.
- Fill gout prophylaxis, fexofenadine, acetaminophen, and folic acid prescriptions, as needed.
- Inquire about AEs.
- Screen failure subjects that take MTX during Week -4 or Week -3, and who are females of childbearing potential, will receive a safety follow-up phone call/e-mail/site visit approximately 30 days after the last dose of MTX to verify at least one ovulatory cycle has occurred since the last dose of MTX. If the subject has not ovulated, a urine pregnancy test will be performed. Screen failure subjects who are non-vasectomized males, a phone/e-mail/site visit inquiry will be conducted 3 months after MTX discontinuation regarding partner pregnancy.

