# Examples of an AE include:

- Conditions newly detected or diagnosed after the signing of the ICF, including conditions
  that may have been present but undetected prior to the start of the study
- Conditions known to have been present prior to the start of the study that worsen after the signing of the ICF
- Signs, symptoms, or the clinical sequelae of a suspected drug interaction
- Signs, symptoms, or the clinical sequelae of a suspected overdose of either investigational product or a concomitant medication (overdose per se should not be reported as an AE)

Issues that will not be considered an AE include:

- Conditions present at the start of the study should be recorded as medical history
- Medical or surgical procedures (e.g., endoscopy, appendectomy; however, a condition that leads to a procedure is an AE if it qualifies according to the definitions above)
- Situations where an untoward medical occurrence did not occur (e.g., social, diagnostic, elective, or convenience admission to a hospital)
- Fluctuations of pre-existing disease(s) or condition(s) present or detected at the start of the study that do not represent a clinically significant change from baseline
- Abnormal laboratory or test findings that are not assessed by the Investigator as a clinically significant change from baseline

AEs are divided into the categories "serious" and "non-serious." This determines the procedures that must be used to report/document the AE.

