### 9.5.4.1.2 Documentation of Adverse Events

AE monitoring will begin from the signature of the ICF until the 6 month Post Treatment Follow-up Visit.

SAE monitoring will begin from the signature of the ICF until the 6 month Post Treatment Follow-up Visit.

Subjects will be questioned about AEs at each study visit, using nonspecific questions, such as "How have you been feeling since the last study visit?" AEs must be recorded on the AE eCRF and documented in the source record after the signing of the ICF.

AEs recorded before the first dose of MTX in the Run-In Period will be recorded as medical history.

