### 9.5.4.5 Physical Examinations

A complete physical examination will be performed at the Screening Visit, including assessment of HEENT, heart, lungs, abdomen, skin, extremities, and neurological status. The exam will include assessment for presence of tophi, as well as gout history and symptom severity (Section 2.1).

A targeted physical examination per the investigator judgement but at a minimum should include heart, lungs and abdominal exam and include a joint and skin evaluation and assessment of AEs at Week -4, Day 1, and prior to administration of pegloticase at Weeks 4, 8, 12, 16, 20, 24, 36,

Protocol: HZNP-KRY-201

KRYSTEXXA IND: 010122

Version 3.0, Administrative Change 1

the End of Pegloticase Infusions Visit (if applicable), Week 52/End of Study/Early Termination and 3 and 6 month Post Treatment Follow-up Visits.

Physical examination findings at screening should be recorded on the medical and surgical history eCRF.

Clinically significant findings from the targeted physical examinations will be recorded as AEs.

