#### 9.6.7 Safety Analysis

Treatment-emergent AEs (TEAEs) during the Run-In period are defined as events with an onset date on or after the first dose of MTX through the first pegloticase infusion, or 30 days after the last dose of MTX for subjects who do not receive pegloticase. TEAEs during the Pegloticase + IMM Period are defined as events that occur after the start of the first pegloticase infusion through 30 days after the last dose of pegloticase and/or MTX (whichever is later). TEAEs during the MTX Run-in Period will be summarized with the ITT population, and TEAEs during the Pegloticase + IMM Period will be summarized with both the ITT and mITT populations. TEAEs during any period (MTX Run-in Period or Pegloticase + IMM Period) will be summarized for the mITT population. AEs that occur more than 30 days after the last dose of pegloticase and/or MTX through the 6 month follow-up visit will also be summarized. The number and percentage of subjects experiencing AEs will be summarized by system organ class and preferred term. Summaries by maximum severity and relationship to MTX and pegloticase

Protocol: HZNP-KRY-201

KRYSTEXXA IND: 010122

Version 3.0, Administrative Change 1

will also be provided. SAEs and AEs leading to discontinuation of MTX and pegloticase will be presented by system organ class and preferred term.

Incidence of IRs, gout flares, and other AEs of special interest will be summarized.

Laboratory test results, including urine uric acid:creatinine ratio, will be summarized by study visit and change from baseline. Shift tables for laboratory parameters by Common Terminology Criteria for Adverse Events grade will be presented. Laboratory test results will also be classified relative to the normal reference range (normal, low, or high).

Vital signs, including blood pressure, respiratory rate, temperature, and heart rate, will be summarized by study visit and change from baseline.

Prior and concomitant medications will be summarized and/or included in the data listings.

Data for the MTX Run-in Period and Pegloticase + IMM Period will be summarized separately, where applicable.

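### Two AE-recording thresholds for the same targeted physical examination: the 12 visit lists take any finding, Section 9.5.4.5 and Schedule footnote 7 only clinically significant ones

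*Protocol*

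**What the plan says.** Section 9.5.6 gives site staff a procedure list for each visit. Wherever a targeted examination is listed, the item describes its scope as "heart, lungs and abdominal exam and joint and skin evaluation and assessment of AEs" and then adds "Any finding will be recorded as an AE". The item sets no threshold and does not refer to another section.

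Other parts of the protocol set a narrower rule:

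- Section 9.5.4.5 (Physical Examinations) says "Clinically significant findings from the targeted physical examinations will be recorded as AEs". Footnote 7 of the Schedule of Assessments carries the same sentence.
- The AE definition (Section 9.5.4.1.1.1) says "Conditions present at the start of the study should be recorded as medical history". It also excludes "Fluctuations of pre-existing disease(s) or condition(s) present or detected at the start of the study" where these are changes "that do not represent a clinically significant change from baseline".
- Section 9.5.4.1.2 says "AEs recorded before the first dose of MTX in the Run-In Period will be recorded as medical history".
- Section 9.6.7 defines run-in treatment-emergent AEs as "events with an onset date on or after the first dose of MTX through the first pegloticase infusion". Those of the Pegloticase + IMM Period run from the start of the first infusion to 30 days after the last dose of pegloticase or MTX, whichever is later.

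**The concern.** The AE/SAE profile is a stated safety endpoint (Section 9.6.1.5), reported as the number and percentage of subjects by system organ class and preferred term. What counts as an AE is fixed when the site fills in the eCRF, so a later analysis plan cannot repair a difference in recording between sites.

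The examination covers joints and skin, where long-standing gout shows itself. Footnote 7 also places the tophus assessment within the targeted examination at Weeks 24, 36 and 52 and at both follow-up visits. Staff working from the visit list have an instruction to record every finding, while staff working from Section 9.5.4.5 have an instruction to filter. With approximately 8 centers and 12 to 16 subjects, the AE profile could depend in part on which section a site follows.

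**Working it through.** No sample size, power or event rate enters this point, so the check is mainly a comparison of texts.

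**1. How widespread the sentence is.** The lists with a targeted examination are Week -4, Day 1, and Weeks 4, 8, 12, 16, 20, 24 and 36 (9 lists), plus the End of Pegloticase Infusions Visit, Week 52/End of Study/Early Termination, and the Post Treatment Follow-up (3 lists). That makes 9 + 3 = 12. All 12 carry the sentence, so it is not an isolated slip.

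**2. What each rule does with two example findings at Day 1 or later.**

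| Finding | Visit list, read literally | Section 9.5.4.5 with the AE definition |
|---|---|---|
| Tophus or swollen joint present since before Screening, unchanged | AE | Not an AE; medical history |
| New but clinically insignificant skin sign | AE | Not recorded as an AE |

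In the top row of the table the AE definition matters as well as Section 9.5.4.5, because an unchanged tophus might be called clinically significant in itself. Section 9.5.4.5 also sends Screening examination findings to the medical and surgical history eCRF. Under the literal visit list, the same unchanged sign would be history at Screening and an AE at Day 1.

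**3. Where a wrongly recorded finding would appear.**

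- Week -4 (1 list): MTX is dispensed at this visit. A finding recorded before the first dose goes to medical history under Section 9.5.4.1.2 and does not enter AE incidence.
- Day 1 to Week 52, including the End of Pegloticase Infusions Visit (10 lists): a finding given an onset date at the visit, or recorded as worsened, would be treatment-emergent if it falls within 30 days of the last dose. A chronic sign correctly dated before MTX would be on the AE eCRF but outside the treatment-emergent tables.
- Post Treatment Follow-up (1 list, used at 3 and 6 months): AEs arising more than 30 days after the last dose are summarized separately.

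These add up to 1 + 10 + 1 = 12 lists.

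**4. What one misclassified subject is worth.** Incidence counts subjects, so repeated entries of one sign in one subject add at most one subject per preferred term. With the planned 12 to 16 subjects, that is 1/16 = 6.3% to 1/12 = 8.3%. This shows how sensitive a single table line is. It does not forecast how many subjects would be affected.

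**The case against.** The strongest reply is that the sentence directly follows the assessment of AEs, so an investigator can read it as any finding that meets the AE definition. That definition already excludes pre-existing conditions, Screening findings and gout history are already documented elsewhere, and treatment-emergence depends on onset date. On that reading a chronic sign would enter the tables only through a dating or grading error. This is a fair limit on the consequence. It does not remove the mismatch, because even the mild reading omits the clinical-significance threshold of Section 9.5.4.5, and an instruction repeated in 12 lists should not depend on a charitable reading.

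A reader might infer more than the documents support:

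- *That Week -4 is a second contradiction that adds to AE incidence.* Section 9.5.4.1.2 operates after the visit list: it takes AEs recorded before the first MTX dose and files them as medical history. What is missing at Week -4 is a cross-reference.
- *That all subjects start with tophi and swollen joints.* Tophaceous deposits are one of three alternative qualifying criteria (Section 9.3.1, criterion 7), the flare-prophylaxis text provides for patients without tophi, and no criterion requires swollen joints.
- *That the number of examinations measures the problem.* A completer has 12 targeted examinations, and 12 x 13 subjects = 156. That counts occasions on which a finding might be made. It says nothing about expected AEs and should not be used as a magnitude.

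It is also true that the study is single-arm, so no between-arm safety comparison is distorted, and that the AEs of special interest have their own definitions or confirmation rules.

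**Conclusion.** The inconsistency is established: the same examination has two recording thresholds, and the visit lists are the outliers against Section 9.5.4.5, footnote 7 and the AE definition. If sites follow the lists literally, findings that are not AEs under the rest of the protocol could be entered as AEs, mainly from Day 1 onward, and reported incidence could vary with the section followed.

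A reader might conclude that chronic gout signs will inflate AE incidence. The protocol does not support that as a certainty. It requires that sites apply the sentence literally and also give the sign an onset at the visit or record it as worsened. The protocol gives no frequency of findings, so the net effect is possible but cannot be quantified. The primary endpoint, a serum uric acid laboratory measure, is untouched. This is a consistency defect in safety recording, worth correcting because the correction is simple.

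**What to change.** In each of the 12 visit lists, replace the sentence with the wording already in Section 9.5.4.5, "Clinically significant findings from the targeted physical examinations will be recorded as AEs", and add a cross-reference to Section 9.5.4.5 and the AE definition in Section 9.5.4.1.1.1. Using the existing sentence avoids creating a third wording. At Week -4, also cross-refer to Section 9.5.4.1.2, so that sites know AEs recorded before the first MTX dose go to medical history.

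The cost is one repeated text edit in the next amendment. It adds no assessments and no site work, and it spares sites from grading severity and judging relatedness for entries that the rest of the protocol does not treat as AEs.

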## 9.5.6.1.3 Week -2

- Confirm study eligibility through review of the inclusion/exclusion criteria (see Section 9.3).
- Obtain blood samples for hematology and clinical chemistry analysis.
- Obtain a urine sample for uric acid:creatinine ratio.
- Obtain a urine sample from all females of childbearing potential for performance of a pregnancy test.
- Obtain a blood sample for measurement of sUA (only 1 sample for central laboratory).
- Assess MTX compliance and re-dispense MTX.

KRYSTEXXA IND: 010122

- Document gout flares and intensity.
- Ask Yes/No question regarding folic acid and gout flare prophylaxis compliance.
- Fill gout prophylaxis, fexofenadine, acetaminophen, and folic acid prescriptions, as needed.
- Collect substance use history, and medication history (see Section 9.4.9 for restrictions regarding medications).
- Inquire about AEs.
- Screen failure subjects that taken MTX during Week -4 or Week -3, Week -2 or Week -1, and who are females of childbearing potential, will receive a safety follow-up phone call/e-mail/site visit approximately 30 days after the last dose of MTX to verify at least one ovulatory cycle has occurred since the last dose of MTX. If the subject has not ovulated, a urine pregnancy test will be performed. Screen failure subjects who are non-vasectomized males, a phone/e-mail/site visit inquiry will be conducted 3 months after MTX discontinuation regarding partner pregnancy.

# 9.5.6.2 Pegloticase + IMM Period

# 9.5.6.2.1 Day 1

On Day 1, subjects will return to the clinic for the following assessments and the first dose of pegloticase.

- Obtain 1 blood sample for measurement of sUA prior to the pegloticase infusion.
- Confirm study eligibility through review of the inclusion/exclusion criteria (see Section 9.3).
- Administer MTX ≥60 minutes prior to pegloticase infusion if subject has not taken MTX within the previous 1 to 3 days.
- Perform a targeted physical examination should include heart, lungs and abdominal exam and joint and skin evaluation and assessment of AEs. Any finding will be recorded as an AE.
- Document gout flares and intensity.
- Record vital signs (blood pressure [prior and post infusion], respiratory rate, temperature, and heart rate [prior and post infusion]), including measurement of weight prior to infusion (see Section 9.5.4.4).
- Perform 12-lead ECG prior to the pegloticase infusion.

KRYSTEXXA IND: 010122 Protocol: HZNP-KRY-201 Version 3.0, Administrative Change 1

• Collect swollen/tender joint counts; administer HAQ; and record patient and physician global assessments and joint pain assessment responses.

- Assess MTX compliance and re-dispense MTX.
- Ask Yes/No question regarding folic acid, gout flare prophylaxis, and IR prophylaxis compliance.
- Fill gout prophylaxis, fexofenadine, acetaminophen, and folic acid prescriptions, as needed.
- Obtain blood samples for hematology and clinical chemistry analysis.
- Obtain a urine sample for uric acid:creatinine ratio.
- Obtain a urine sample from all females of childbearing potential for performance of a pregnancy test.
- Obtain blood samples for MTX Polyglutamate analysis prior to the infusion.
- Obtain blood samples for anti-PEG and anti-uricase IgG antibodies prior to the infusion.
- Obtain blood samples for pegloticase PK analysis prior to the infusion.
- Administer IR prophylaxis (i.e., fexofenadine, acetaminophen, and methylprednisolone or hydrocortisone) (see Section 9.4.1.3).
- Administer the first dose of pegloticase and record date, volume, and duration of infusion, and start/stop (inclusive of 10-mL flush) times of dosing.
- Obtain a blood sample (1 sample) for measurement of sUA after the end of the pegloticase infusion prior to discharge.
- Obtain blood samples for pegloticase PK analysis after the end of the infusion prior to discharge.
- Inquire about AEs and concomitant medication use.
- Perform DECT (if applicable).

# 9.5.6.2.2 Week 1 (Non-infusion visit for those who consent only)

- Inquire about AEs and concomitant medication use.
- Obtain blood samples for pegloticase PK analysis.

KRYSTEXXA IND: 010122 Protocol: HZNP-KRY-201 Version 3.0, Administrative Change 1

Obtain blood samples for anti-PEG and anti-uricase IgG antibodies.

Obtain a blood sample (1 sample) for measurement of sUA.

### 9.5.6.2.3 Week 2

- Obtain 2 blood samples for measurement of sUA within 48 hours prior to this visit's pegloticase infusion. Pre-infusion sUA results must be reported by the local or central laboratory prior to pegloticase infusion. If a local laboratory sample is drawn at a center other than the research site (within 48 hours prior to the pegloticase infusion), a sample for the central laboratory will be drawn prior to the pegloticase infusion on the day of the visit (see Section 9.5.1.1).
- Administer MTX ≥60 minutes prior to pegloticase infusion if subject has not taken MTX within the previous 1 to 3 days.
- Document gout flares and intensity.
- Record vital signs (blood pressure [prior and post infusion], respiratory rate, temperature, and heart rate [prior and post infusion]) (see Section 9.5.4.4).
- Assess MTX compliance and re-dispense MTX.
- Ask Yes/No question regarding folic acid, gout flare prophylaxis, and IR prophylaxis compliance.
- Fill gout prophylaxis, fexofenadine, acetaminophen, and folic acid prescriptions, as needed.
- Obtain blood samples for hematology and clinical chemistry analysis.
- Obtain a urine sample for uric acid:creatinine ratio.
- Obtain a urine sample from all females of childbearing potential for performance of a pregnancy test.
- Obtain blood samples for pegloticase PK analysis prior to the infusion.
- Obtain blood samples for anti-PEG and anti-uricase IgG antibodies prior to the infusion.
- Administer IR prophylaxis (i.e., fexofenadine, acetaminophen, and methylprednisolone or hydrocortisone) (see Section 9.4.1.3).
- Administer pegloticase and record date, volume, and duration of infusion, and start/stop (inclusive of 10-mL flush) times of dosing.

Protocol: HZNP-KRY-201 Version 3.0, Administrative Change 1

KRYSTEXXA IND: 010122

• Obtain a blood sample (1 sample) for measurement of sUA after the end of pegloticase infusion prior to discharge.

- Obtain blood samples for pegloticase PK analysis after the end of the infusion prior to discharge
- Inquire about AEs and concomitant medication use.

#### 9.5.6.2.4 Week 4

- Obtain 2 blood samples for measurement of sUA within 48 hours prior to this visit's pegloticase infusion. Pre-infusion sUA results must be reported by the local or central laboratory prior to pegloticase infusion. If a local laboratory sample is drawn at a center other than the research site (within 48 hours prior to the pegloticase infusion), a sample for the central laboratory will be drawn prior to the pegloticase infusion on the day of the visit (see Section 9.5.1.1).
  - Stopping Rule: Subjects with an sUA level >6 mg/dL at 2 consecutive study visits beginning with the Week 2 Visit (not including post-infusion samples) will discontinue treatment and remain in the study.
- Administer MTX ≥60 minutes prior to pegloticase infusion if subject has not taken MTX within the previous 1 to 3 days.
- Perform a targeted physical examination should include heart, lungs and abdominal exam and joint and skin evaluation and assessment of AEs. Any finding will be recorded as an AE.
- Document gout flares and intensity.
- Record vital signs (blood pressure [prior and post infusion], respiratory rate, temperature, and heart rate [prior and post infusion]) (see Section 9.5.4.4).
- Assess MTX compliance and re-dispense MTX.
- Obtain blood samples for MTX Polyglutamate analysis prior to the infusion.
- Obtain blood samples for pegloticase PK analysis prior to the infusion.
- Obtain blood samples for anti-PEG and anti-uricase IgG antibodies prior to the infusion
- Ask Yes/No question regarding folic acid, gout flare prophylaxis, and IR prophylaxis compliance.
- Fill gout prophylaxis, fexofenadine, acetaminophen, and folic acid prescriptions, as needed.

Protocol: HZNP-KRY-201 Version 3.0, Administrative Change 1

KRYSTEXXA IND: 010122

• Obtain a urine sample from all females of childbearing potential for performance of a pregnancy test.

- Administer IR prophylaxis (i.e., fexofenadine, acetaminophen, and methylprednisolone or hydrocortisone) (see Section 9.4.1.3).
- Administer pegloticase and record date, volume, and duration of infusion, and start/stop (inclusive of 10-mL flush) times of dosing.
- Obtain blood samples for pegloticase PK analysis after the end of the infusion prior to discharge.
- Obtain a blood sample (1 sample) for measurement of sUA after the end of pegloticase infusion prior to discharge.
- Inquire about AEs and concomitant medication use.

### 9.5.6.2.5 Week 6

- Obtain 2 blood samples for measurement of sUA within 48 hours prior to this visit's pegloticase infusion. Pre-infusion sUA results must be reported by the local or central laboratory prior to pegloticase infusion. If a local laboratory sample is drawn at a center other than the research site (within 48 hours prior to the pegloticase infusion), a sample for the central laboratory will be drawn prior to the pegloticase infusion on the day of the visit (see Section 9.5.1.1).
  - Stopping Rule: Subjects with an sUA level >6 mg/dL at 2 consecutive study visits beginning with the Week 2 Visit (not including post-infusion samples) will discontinue treatment and remain in the study.
- Administer MTX ≥60 minutes prior to pegloticase infusion if subject has not taken MTX within the previous 1 to 3 days.
- Document gout flares and intensity.
- Record vital signs (blood pressure [prior and post infusion], respiratory rate, temperature, and heart rate [prior and post infusion]) (see Section 9.5.4.4).
- Assess MTX compliance and re-dispense MTX.
- Ask Yes/No question regarding folic acid, gout flare prophylaxis, and IR prophylaxis compliance.
- Fill gout prophylaxis, fexofenadine, acetaminophen, and folic acid prescriptions, as needed.

Protocol: HZNP-KRY-201 Version 3.0, Administrative Change 1

KRYSTEXXA IND: 010122

 Obtain a urine sample from all females of childbearing potential for performance of a pregnancy test.

- Obtain blood samples for hematology and clinical chemistry analysis.
- Obtain a urine sample for uric acid:creatinine ratio.
- Obtain blood samples for pegloticase PK analysis prior to the infusion.
- Obtain blood samples for anti-PEG and anti-uricase IgG antibodies prior to the infusion.
- Administer IR prophylaxis (i.e., fexofenadine, acetaminophen, and methylprednisolone or hydrocortisone) (see Section 9.4.1.3).
- Administer pegloticase and record date, volume, and duration of infusion, and start/stop (inclusive of 10-mL flush) times of dosing.
- Obtain a blood sample (1 sample) for measurement of sUA after the end of pegloticase infusion prior to discharge.
- Obtain blood samples for pegloticase PK analysis after the end of the infusion prior to discharge.
- Inquire about AEs and concomitant medication use.

